Attachment 4. Subject Diaries Ver 1.0 (2018/07/26)

BUKU HARIAN SUBJEK

VISIT (TANGGAL BUKU HARIAN DIBAGIKAN)	 Visit 2  Visit 3  Visit 4
TANGGAL VISIT	— — — — DD MM YY
NOMOR SUBJEK	R
INISIAL SUBJEK	
TANDA TANGAN SUBJEK	

Jangan lupa membawa buku ini
setiap mengunjungi Rumah
Sakit

Anda sedang berpartisipasi dalam uji klinis DWP14012 penyakit refluks gastroesofageal erosif (GERD). Buku harian subjek ini dirancang untuk menilai tingkat keparahan dan frekuensi gejala penyakit refluks gastroesofageal erosif Anda. Materi ini akan digunakan sebagai data untuk mengevaluasi efektivitas dan keamanan dari DWP14012, oleh karena itu, harap baca panduan berikut dengan cermat sebelum mencatat dan mengisi dengan teliti agar tidak melewatkannya bagian apapun.

– Petunjuk Pengisian –

- ✓ Anda akan mengevaluasi gejala utama penyakit refluks gastroesofageal ① "heartburn" dan ② "refluks asam lambung", serta gejala atipikal ③ "batuk kronis" dan ④ "sensasi mengganggu di tenggorokan" dua kali sehari (siang/malam) dan mencatatnya dalam buku harian subjek. Selain itu, catat ⑤ 'apakah Anda terbangun selama tidur karena "heartburn" dan refluks asam lambung.'
- ✓ **① "Heartburn"** didefinisikan sebagai ketidaknyamanan atau rasa panas atau nyeri seperti sensasi terbakar di dada.
- ✓ **② "Refluks asam lambung"** didefinisikan sebagai naiknya cairan asam atau pahit ke tenggorokan atau mulut, atau rasa asam dan pahit di mulut.
- ✓ **③ "Batuk kronis"** didefinisikan sebagai batuk kering yang menetap dan terus menerus, tanpa dahak dan iritasi atau gangguan pada tenggorokan disertai dengan naiknya cairan asam atau pahit dari lambung.
- ✓ **④ "Sensasi mengganggu di tenggorokan"** didefinisikan sebagai perasaan seolah ada sesuatu yang mengganjal di tenggorokan.

✓ Pada bagian “Siang hari” di buku harian, catat gejala yang Anda rasakan dalam satu hari sebelum tidur, sesuai kriteria di bawah

✓ Pada bagian “Malam hari” di buku harian, catat gejala yang Anda rasakan selama malam hari saat bangun di pagi hari berikutnya. Apabila Anda mengalami beberapa gejala. Tulislah gejala yang dirasa paling tidak nyaman dan menyakitkan.

✓ Gejala “Heartburn” dan “refluks asam lambung” dinilai berdasarkan skala 0 hingga 4, dengan kriteria sebagai berikut.

Penilaian gejala “siang hari” (waktu beraktivitas)

0	Tidak ada	Tidak ada gejala
1	Ringan	Gejala dirasakan tetapi tidak ada rasa tidak nyaman
2	Sedang	Sedikit ketidaknyamanan dan sedikit keterbatasan dalam aktivitas normal sehari-hari
3	Berat	Gejala sering dirasakan, dan sering terjadi keterbatasan dalam aktivitas normal sehari-hari
4	Sangat Berat	Gejala yang terus menerus dan keterbatasan yang signifikan terhadap aktivitas normal sehari-hari

Penilaian gejala “malam hari” (waktu tidur)

0	Tidak ada	Tidak ada gejala
1	Ringan	Gejalanya terasa, namun bisa diabaikan dan tidak mengganggu tidur
2	Sedang	Sedikit ketidaknyamanan, sedikit gangguan pada tidur
3	Berat	Gejalanya sering dirasakan, dan sering terjadi gangguan tidur
4	Sangat Berat	Gejalanya dirasakan terus menerus, dan sulit tidur

– Perhatian –

- ✓ Gunakan pulpen berwarna hitam jika memungkinkan, dan saat mengubah isi, coret area yang perlu diperbaiki dengan garis lurus, tulis perbaikannya, tanggal dilakukan perbaikan, alasan perbaikan, dan kemudian tandatangani. Harap gunakan tanda tangan yang sama dengan tanda tangan di sampul buku.

Contoh) **LAR** LAK 16/04/2017, salah tulis, (tanda tangan)

- ✓ Obat penelitian harus diminum sekali sehari tanpa mempertimbangkan waktu makan dan sebaiknya diminum pada waktu yang tetap. Mohon cantumkan di buku harian subjek jika Anda sudah mengonsumsinya. Pada kunjungan berikutnya, Anda harus mengembalikan kotak obat, sisa obat yang belum digunakan, dan kemasan obat yang sudah kosong.
- ✓ Saat kunjungan berikutnya, pastikan untuk membawa formulir aplikasi Anda.
- ✓ Kami meminta kerjasama Anda dengan staf medis hingga akhir studi ini. Jika Anda mengalami ketidaknyamanan atau kejadian yang tidak diharapkan selama periode uji klinis, mohon beri tahu staf medis penelitian.

Peneliti atau perawat penelitian	Kontak

Hari ke- ()		Tanggal:	Bulan:	Tahun:	
Apakah Anda sudah mengonsumsi obat investigasi uji klinis?					
 Siang hari (diisi sebelum tidur di malam hari)		 Malam hari (diisi setelah bangun tidur di pagi hari)			
Nyeri ulu hati	 Tidak ada  Ringan  Sedang  Berat  Sangat berat		Nyeri ulu hati	 Tidak ada  Ringan  Sedang  Berat  Sangat berat	
Refluks asam lambung	 Tidak ada  Ringan  Sedang  Berat  Sangat berat		Refluks asam lambung	 Tidak ada  Ringan  Sedang  Berat  Sangat berat	
Batuk kronis	 Tidak  Ya		Batuk kronis	 Tidak  Ya	
Sensasi mengganggu di tenggorokan	 Tidak  Ya		Sensasi mengganggu di tenggorokan	 Tidak  Ya	
			Pernahkah Anda terbangun dari tidur karena gejala “nyeri ulu hati” atau “refluks asam lambung”?	 Tidak  Ya	

Memo

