8.4.1.3 Exploratory Endpoints

Assessment on symptoms based on the diary of subjects.

- Proportions of subjects who have not been awakened during sleep for heartburn or acid regurgitation for first 3 days, 7 days, 4 weeks, and 8 weeks (or based on the day Investigator's need) after the first IP administration.

- Proportions of subjects who have relieved from chronic cough for first 3 days, 7 days, 4 weeks, and 8 weeks (or based on the day Investigator's need) after the first IP administration daytime and nighttime.
- Proportions of subjects who have relieved from irritating feeling in the throat for full 3 days, 7 days, 4 weeks, and 8 weeks (or based on the day Investigator's need) after the first IP administration daytime and nighttime.
(Week 8 evaluation will only be applicable to patient receiving treatment 2)

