8.4.2.2 Assessment on symptoms based on the diary of subjects

The subjects will self-assess each symptom of 'heartburn' and 'acid regurgitation' (major symptoms of gastroesophageal reflux disease) twice daily (daytime/nighttime combined) in the subject diary which then will be collected and analyzed. In addition, the presence of 'chronic cough' and 'foreign body sensation in the throat' which are non-typical symptoms of gastroesophageal reflux disease will be assessed twice daily (daytime/nighttime combined), and any experience of awakening during sleep for heartburn or acid regurgitation will be collected.

The scale (0 to 4) for scores of assessing daytime/nighttime combined symptoms of 'heartburn' and 'acid regurgitation' is as follows:

Assessment on daytime symptoms		
0	None	No symptoms
1	Mild	Symptoms noticeable, but not bothersome
2	Moderate	A little bothersome and some limitations of daily activities
3	Severe	Symptoms noticeable for a lot of time and frequent limitations of daily activities
4	Very severe	Symptoms persistent and considerable limitations of daily activities

Assessment on nighttime symptoms		
0	None	No symptoms
1	Mild	Symptoms noticeable, but can be ignored, and do not disturb sleep
2	Moderate	A little bothersome and some disturbance of sleep
3	Severe	Symptoms noticeable for a lot of time and frequent disturbance of sleep
4	Very severe	Symptoms persistent and difficulties in sleeping

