9.2.3.3 Exploratory Endpoints

Assessment on symptoms based on the diary of subjects.

- The proportions (%) of subjects who have not been awakened during sleep for heartburn or acid regurgitation for the first 7 days, full 4 weeks, and full 8 weeks after the first IP administration and its 95% confidence interval will be presented by treatment group. To compare the control group and study group, the 2-sided 95% confidence intervals and p-value will be obtained by using the Cochran-Mantel-Haenszel method.
- The proportions (%) of subjects who have relieved from chronic cough for the first 7 days, full 4 weeks, and full 8

weeks after the first IP administration and its 95% confidence interval will be presented by treatment group. To compare the control group and study group, the 2-sided 95% confidence intervals and p-value will be obtained by using the **Chi Square test or Fisher's Exact test method**.

- The proportions (%) of subjects who have relieved from foreign body sensation for the first 7 days, full 4 weeks, and full 8 weeks after the first IP administration and its 95% confidence interval will be presented by treatment group. To compare the control group and study group, the 2-sided 95% confidence intervals and p-value will be obtained by using the **Chi Square test or Fisher's Exact test method**.

(Week 8 evaluation will only be applicable to patient receiving treatment 2)

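### The diary describes chronic cough as accompanied by rising acid or bitter fluid, so an exploratory endpoint named cough relief can partly record regurgitation instead

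*Combined protocol and SAP*

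**What the plan says.** The instructions in Attachment 4 define each diary item before the daily pages.

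- Definition 2, acid reflux: "didefinisikan sebagai naiknya cairan asam atau pahit ke tenggorokan atau mulut, atau rasa asam dan pahit di mulut" (acid or bitter fluid rising to the throat or mouth, or an acid and bitter taste).
- Definition 3, chronic cough (*batuk kronis*): "batuk kering yang menetap dan terus menerus, tanpa dahak dan iritasi atau gangguan pada tenggorokan disertai dengan naiknya cairan asam atau pahit dari lambung" (a persistent, continuous dry cough, without phlegm, then a clause on throat irritation or disturbance, then a clause on acid or bitter fluid rising from the stomach).
- Definition 4, disturbing sensation in the throat: "didefinisikan sebagai perasaan seolah ada sesuatu yang mengganjal di tenggorokan" (a feeling that something is stuck there). No reflux condition is attached.

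The daily page gives cough one *Tidak*/*Ya* (no/yes) box for the day and one for the night. It has no separate box for cough without reflux.

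The protocol body is plainer. Section 8.4.2.2 records "the presence of 'chronic cough' and 'foreign body sensation in the throat' which are non-typical symptoms of gastroesophageal reflux disease", twice daily and with no reflux condition. Section 8.4.1.3 lists as exploratory "Proportions of subjects who have relieved from chronic cough for first 3 days, 7 days, 4 weeks, and 8 weeks". Section 9.2.3.3 analyses "The proportions (%) of subjects who have relieved from chronic cough for the first 7 days" and the later periods, with a 95% confidence interval by group and a between-group comparison.

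**The concern.** The protocol names the endpoint as relief of chronic cough and treats cough as a symptom distinct from regurgitation. The diary text describes cough together with regurgitation, in nearly the words it uses for the acid-reflux item, and adds a throat clause that overlaps item 4. The item that subjects are told to score is therefore not the item that the analysis section names.

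At stake is the interpretation of one exploratory comparison. A treatment that reduces regurgitation more than its comparator could show a cough benefit without changing cough, and cough without regurgitation could go unrecorded. A benefit on an extra-oesophageal symptom is the kind of result that gets quoted even from an exploratory table.

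**Working it through.** The documents give no figure for the cough endpoint, so there is nothing to reproduce. The check sets the texts side by side and then uses a small illustration with assumed values.

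**1. Overlap of definitions.** Definitions 2 and 3 both turn on acid or bitter fluid rising. Definition 4 does not. Sections 8.4.2.2, 8.4.1.3 and 9.2.3.3 do not attach it to cough either.

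**2. How the Indonesian can be read.** The sentence allows at least three parses.

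- The rising-fluid clause qualifies the whole cough. Reflux is then required for *Ya*. This is the natural reading.
- It qualifies only the throat irritation. Irritation with reflux is then still part of the definition.
- *Tanpa* (without) governs both phlegm and irritation. Cough with reflux-related irritation is then excluded, and any distortion could run the other way.

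None of the three describes cough alone.

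**3. Consequence of literal application, natural reading.**

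- A subject coughs and regurgitates at the start, regurgitation stops and the cough continues. *Tidak* is then a correct answer to the diary text.
- A subject has heartburn and cough but no regurgitation. Inclusion criterion 2 (section 3.2) admits such a subject, because frequent heartburn or frequent acid reflux will do alongside the GERD-Q threshold. *Tidak* is correct from the first day, and depending on how relief is defined this subject could count as relieved.

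**4. Illustration (assumed values, not from the documents).** Take subjects whose cough is accompanied by regurgitation at the start, all applying the text literally. Let c be the share whose cough truly resolves, and r the share of the remaining coughers whose regurgitation stops.

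Apparent relief = c + (1 − c) × r

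| c | r = 20% | r = 50% | r = 80% |
|---|---|---|---|
| 0% | 20% | 50% | 80% |
| 20% | 36% | 60% | 84% |
| 40% | 52% | 70% | 88% |

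For example, 0.20 + 0.80 × 0.50 = 0.60.

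With the same c in both arms, the spurious arm difference is (1 − c) × (difference in r). For a 10-point difference in r:

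- c = 0%: 1.00 × 10 = 10 points
- c = 20%: 0.80 × 10 = 8 points
- c = 40%: 0.60 × 10 = 6 points

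These values apply among coughers. They shrink in proportion if only some subjects apply the text literally, or if the denominator includes subjects without cough, and vanish if nobody applies it literally.

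**5. Is an arm difference in regurgitation plausible?** The protocol's phase 2 account is mixed. Section 1.4 reports no significant difference on acid regurgitation when the symptoms were analysed separately. Section 1.6 reports a significant 8-week difference for fexuprazan 40 mg in all nighttime symptoms, acid regurgitation among them. Cough has its own nighttime box, so spill-over is possible but not established.

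**The case against.** The strongest reply is that no rule in the documents scores cough this way. The daily page asks only about *batuk kronis*, *Tidak* or *Ya*, and does not repeat the definition, so a persistent cougher without acid may well tick *Ya*. The syntax is ambiguous, and relief has no operational definition in 8.4.1.3 or 9.2.3.3. A reader might infer from definition 3 that cough becomes relieved whenever regurgitation stops. The documents do not support that. It is a possible result of literal application, not a scoring rule, and this part of the reply stands. It does not remove the problem: the diary tells subjects to read the guide carefully before recording, and section 8.3.14 provides training on completion. If some subjects apply the definition and others the label, the item measures different things in different people.

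A second reply is that the diary may deliberately restrict cough to reflux-associated cough, since section 8.4.2.2 lists cough as an atypical symptom of the disease. No section states such a restriction, and the endpoint is named chronic cough without qualification. This reply does not stand.

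A reader might also try to size the effect from the phase 2 percentages in section 1.4. Those percentages count freedom from any major symptom, heartburn included, and heartburn is not in the cough definition. The same section reports no significant difference on regurgitation alone. They cannot serve as an estimate here.

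The last reply is that the endpoint is exploratory. That is correct, and it limits the weight of the point.

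**Conclusion.** The mismatch is real: the diary's definition of chronic cough carries a reflux clause and an ambiguous throat clause that the protocol's assessment method and endpoint do not. Misclassification can follow when subjects apply the definition as written, and an arm difference in regurgitation can then show as a difference in cough relief.

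Its size cannot be determined from the documents, which give no cough prevalence and no indication of how subjects answer the form. The 6- to 10-point range holds only under the assumptions in the working: literal application, cough accompanied by regurgitation at the start, equal true cough relief of 0% to 40% in both arms, and a 10-point difference in regurgitation cessation.

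The GERD-Q primary endpoint, its non-inferiority test, the sample size and the secondary endpoints are not affected. This is a correction worth making to one exploratory item, not a threat to the trial's main conclusion.

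**What to change.** Delete the throat-irritation clause and the rising-fluid clause from diary definition 3, so that it ends after *tanpa dahak* and cough is recorded whether or not acid rises. This resolves all three parses and matches section 8.4.2.2.

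For diaries already completed:

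- Cross-tabulate cough against the acid-reflux item for the same day or night period. Many *Ya* ticks with reflux marked absent would show that subjects did not apply the reflux condition. Few such ticks would be consistent with literal application but would not prove it, and cough that was never ticked cannot be recovered.
- Do not pool the two diary versions on this item without noting the version.
- Report the item from the uncorrected diary as possibly reflux-associated cough, not as relief of chronic cough.

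The cost is a diary reprint and a version difference on one exploratory item.

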9.2.3.2 Secondary Efficacy Assessment

1. Proportions of subjects with symptoms relief at week 8 measured by GERD-Q Score <8

The proportions of subjects with symptoms relief by Week 8 and their 95% confidence intervals will be provided by group. The proportions of subjects with symptoms relief by Week 8 will be calculated as the cumulative symptoms relief by using the results at the time of final observation including the Withdrawal visit. To compare the control group and study group, the lower bound of the 2-sided 95% confidence intervals will be obtained by using the Chi Square test or Fisher's Exact test method. If this lower bound is greater than the non-inferiority margin of -0.1, the study group will be judged to be non-inferior to the control group. (Week 8 evaluation will only be applicable to patient receiving treatment 2)

2. Assessment on symptoms based on the diary of subjects

- CR (disappearance of heartburn, acid regurgitation, or heartburn/acid regurgitation for 7 consecutive days) is defined as the symptom score of 0 for 7 consecutive days for the first time after the first dose, and the survival time is defined as the time to reach Complete Response (CR) after the first IP administration. Kaplan-Meier plots will be drawn by treatment group, and the medians and their 2-sided 95% confidence intervals will be presented. To compare the control group and study group, the log-rank test will be used.
- The number of subjects without any heartburn, acid regurgitation, or heartburn/acid regurgitation for the first 7 days, full 4 weeks, and full 8 weeks from the first IP administration, the proportion (%) of these subjects and its 95% confidence interval will be presented by treatment group. To compare the control group and study group, the 2-sided 95% confidence intervals and p-value will be obtained by using the Chi Square test or Fisher's Exact test method.

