- Descriptive statistics (mean, standard deviation, median, minimum, and maximum) of the proportions of days free of any heartburn, acid regurgitation, or heartburn/acid regurgitation for the first 7 days, full 4 weeks, and full 8 weeks from the first IP administration will be presented for daytime, nighttime, and daytime/nighttime by group. For comparison between treatment groups, an ANCOVA model will be applied with treatment group as a treatment effect. The results of ANCOVA model will be summarized as the LSM differences between the study group and the control group, the corresponding 2-sided 95% confidence interval, and p-value.
(Week 8 evaluation will only be applicable to patient receiving treatment 2)

3. Assessment on symptoms of reflux disease using GERD-Q

Descriptive statistics (mean, standard deviation, median, minimum, and maximum) for the changes from baseline in frequency at the first 7 days, 4 weeks, and 8 weeks will be presented by time point. For the changes from baseline in variables measured at the first 7 days, 4 weeks, and 8 weeks after the IP administration, an ANCOVA model including treatment group as treatment effect, and baseline value will be applied. The results of ANCOVA model will be summarized as the least squares mean (LSM) and standard error by treatment group, the LSM differences between the study group and the control group, the corresponding 2-sided 95% confidence interval, and p-value
(Week 8 evaluation will only be applicable to patient receiving treatment 2)

4. Quality of life assessment using GERD-HRQL

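### The diary's night instruction asks for the most bothersome symptom when there are several, while the analysis needs every symptom scored, so night-time freedom from a single symptom may be overstated or missing

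*Combined protocol and SAP*

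**What the plan says.** **Diary (Attachment 4, instructions for completion).** The night bullet tells the subject to record on waking what was felt during the night: "catat gejala yang Anda rasakan selama malam hari saat bangun di pagi hari berikutnya". It then adds: "Apabila Anda mengalami beberapa gejala. Tulislah gejala yang dirasa paling tidak nyaman dan menyakitkan". In translation: if you experience several symptoms, write the symptom felt as most uncomfortable and painful. The daytime bullet has no such sentence.

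**Method of assessment (Section 8.4.2.2).** "The subjects will self-assess each symptom of 'heartburn' and 'acid regurgitation", as "major symptoms of gastroesophageal reflux disease) twice daily (daytime/nighttime combined) in the subject diary which then will be collected and analyzed". Separate 0–4 scales are given for day and night.

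**Analysis (Section 9.2.3.2, item 2).** Three diary endpoints are each listed for heartburn, for acid regurgitation and for the two together:
- Complete response, which "is defined as the symptom score of 0 for 7 consecutive days for the first time after the first dose".
- Symptom-free subjects: "The number of subjects without any heartburn, acid regurgitation, or heartburn/acid regurgitation for the first 7 days", with 4-week and 8-week versions.
- Symptom-free time: "proportions of days free of any heartburn, acid regurgitation, or heartburn/acid regurgitation", which "will be presented for daytime, nighttime, and daytime/nighttime by group".

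**Elsewhere in the diary.** The first bullet asks for all four symptoms (heartburn, reflux, chronic cough, throat sensation) twice daily, and the introduction asks that no part be missed. The night page has a separate row for each symptom. The heartburn and reflux rows carry a none box (*Tidak ada*), and the cough and throat rows are yes/no.

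**The concern.** The night sentence asks for one symptom to be written down on exactly the nights when the analysis needs two or more ratings. If a subject obeys it, the less bothersome symptom either has no rating or appears as absent. A false none looks like valid data and cannot be detected later. A blank is visible, but the plan has no specific rule for scoring it.

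The results at stake are the single-symptom night-time ones. They matter because Sections 1.4 and 1.6 rest much of the case for fexuprazan 40 mg on night-time symptoms and report phase 2 results separately for heartburn and regurgitation. Day and night would also be recorded under different rules, which weakens any comparison between the two.

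The rating cannot be recovered from other data. GERD-Q is a 7-day recall of the number of days with symptoms and has no night-time rating for each symptom.

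**Working it through.** The plan states no figure to reproduce here. The check compares the texts and then gives an illustration of size.

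**1. What each text requires on a night with both heartburn and regurgitation**

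| Source | Requirement |
|---|---|
| Diary, night bullet | Write the worst symptom |
| Diary, first bullet and night rows | Rate each symptom |
| Section 8.4.2.2 | Score each symptom 0–4 |
| Section 9.2.3.2 | Needs a score for each symptom |

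The night bullet is the only text written for this case, and it is the one that disagrees with the rest.

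**2. What happens to the other row**

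- *Every row completed:* no effect.
- *Row left blank:* Section 9.2.1 provides LOCF for continuous efficacy endpoints and censoring for survival analysis. It does not say whether a night with one blank row counts as free of that symptom, as not free, or not at all.
- *None ticked:* the night is scored free of a symptom that was present.

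**3. Illustration for the none-ticked case, night-only results**

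Let b be the share of nights with both symptoms, and f the share of subjects who follow the sentence and tick none. Assume that each symptom is equally often the milder one, and that b does not depend on whether the subject follows the sentence. Then:

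overstatement of nights free of one given symptom = b × f × 0.5

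The documents give neither b nor f, so both are assumed over a range.

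| b | f = 0.25 | f = 0.50 | f = 1.00 |
|---|---|---|---|
| 0.10 | 1.25 points | 2.5 | 5 |
| 0.20 | 2.5 | 5 | 10 |
| 0.30 | 3.75 | 7.5 | 15 |
| 0.40 | 5 | 10 | 20 |

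For example, 0.20 × 0.50 × 0.5 = 0.05, or 5 points. With an uneven split, one symptom is overstated by more and the other by less, but the two still sum to b × f.

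**4. Blank rows**

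Let d be the share of nights whose row is blank because another symptom was worse, and p the true share of nights free of the symptom. Scoring blanks as 0 gives p + d. Dropping them from the denominator gives p/(1 − d), an excess of p·d/(1 − d). The blank nights were symptomatic, so p + d cannot exceed 1, and this excess is at most d. Treating blanks as missing therefore does no worse than scoring them 0 and usually does better, but it does not remove the error. Only completed rows do that.

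**5. Which results are exposed**

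Symptom-free days give 3 symptom definitions × 3 periods × 3 times of day = 27 comparisons.
- Single-symptom and night-only: 2 × 3 × 1 = 6. The formula in step 3 applies to these.
- Single-symptom and day/night combined: another 6. They change only when the masked symptom was also absent by day, so the effect is smaller.
- Symptom-free subjects (2 × 3 = 6 of 9 comparisons) and complete response (2 of 3 definitions) are touched only if every occurrence of the symptom in the window was at night and masked.

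**6. The combined heartburn/regurgitation result**

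If one of these two is the worst symptom, it is still recorded and the night counts as symptomatic. If cough or throat sensation is worst, literal obedience can leave both major symptoms unrecorded. The combined result is largely but not fully protected. The night-time cough and throat items behind the exploratory endpoints (Section 8.4.1.3) are exposed in the same way.

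**The case against.** The strongest reply is that the form mostly corrects itself. Its first bullet, its introduction and its separate rows all ask for every symptom, and the bullet after the disputed sentence gives the 0–4 scale for both heartburn and reflux. The sentence does not contain the word only and does not tell anyone to mark the rest as absent. Since none is defined as no symptoms, ticking it while symptomatic would break the scale, so a literal reader is more likely to leave a blank. The author may well have meant the worst severity of each symptom. Section 8.3.14 already provides diary training at Visit 2 and a completion check at Visit 3.

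Most of this stands as a limit on size. Many subjects will probably complete every row, so loss of data is a risk and not a certainty. It does not remove the contradiction, which each subject has to resolve alone. The planned training does not mention the sentence, and a completion check can find a blank but not a false none.

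A reader might go further and infer that the arms are biased in a known direction. Phase 2 (Section 1.4) found more heartburn-free days on fexuprazan 40 mg and no significant difference for regurgitation. If that recurred, heartburn would hide regurgitation less often in that arm. This is possible, but both arms use the same diary, and the documents do not give the frequency of nights with both symptoms, the dominant symptom by arm, or how many subjects would follow the sentence. The direction cannot be stated.

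**Conclusion.** The diary's night instruction conflicts with Sections 8.4.2.2 and 9.2.3.2 and with the rest of the diary. Night-time freedom from a single symptom may be overstated or missing as a result. The size is unknown. About 1 to 20 percentage points for night-only results follows from assumed inputs (10–40% of nights with both symptoms, 25–100% of subjects following the sentence and ticking none, an even split). The top of that range is the case where everyone obeys literally and never leaves a blank. The effect is 0 if all rows are completed.

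Three stronger inferences are not supported. These figures do not carry over to the combined day/night, symptom-free-subject or complete-response results, for the reasons in step 5. The combined-symptom result is not wholly safe, but neither is it broadly compromised. The primary endpoint is GERD-Q below 8 at Week 4 (Section 8.4.1.1); it does not use the diary and is not affected.

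This is a defect in collecting secondary and exploratory data. It should be corrected because the fault is plain and the correction is small.

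**What to change.** Replace the sentence, in the diary's language and in both the day and night bullets, with: *Rate every symptom separately, every day and every night; if a symptom occurs several times, record its worst severity.*

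Then:
- Cover this in the diary training already planned at Visit 2, and query blank rows at the completion check already planned at Visit 3 (Section 8.3.14).
- State in Section 9.2.1 that a blank diary row is treated as missing and not as 0. By step 4 this limits the error but does not replace completed rows.
- If diaries with the present wording are already in use, record which form each subject used. Past nights cannot be reconstructed.

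The cost is one changed sentence and re-issue of the diary form, through the approval route in Section 11.10. No visit, test or staff time beyond the existing training and check is needed.
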